15.4 Vital Signs

All vital sign parameters from the on-treatment period, will be summarized using descriptive statistics (mean, SD, median, Q1, Q3, minimum, and maximum) of actual values and changes from baseline for each visit over time. End of treatment visit will be summarized separately. The changes computed will be the differences from baseline.

The following potentially clinically significant abnormalities will be summarized:

- ≤ 95 mmHg and decrease from baseline ≥ 20 mmHg in systolic blood pressure
- ≥ 140 mmHg and increase from baseline ≥ 20 mmHg in systolic blood pressure
- ≤ 45 mmHg and decrease from baseline ≥ 20 mmHg in diastolic blood pressure
- ≥ 90 mmHg and increase from baseline ≥ 20 mmHg in diastolic blood pressure
- ≤ 50 beats/min and decrease from baseline ≥ 20 beats/min in pulse rate
- ≥ 100 beats/min and increase from baseline ≥ 20 beats/min in pulse rate
- ≤ 20 breaths/min and decrease from baseline ≥ 5 breaths/min in respiratory rate
- ≥ 20 breaths/min and increase from baseline ≥ 5 breaths/min in respiratory rate
- $\geq 10\%$ weight decrease
- $\geq 10\%$ weight increase

The tables in this section may be repeated for China sub-population.

A listing of vital signs including results for oxygen saturation will be provided including participant identifier, age, sex, race, vital sign parameter, visit, timepoint, date, time, value, unit and change from baseline. Baseline values and post-baseline values collected after the on-treatment period will be flagged.

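### SAP 15.4 uses 20 breaths/min as both the low and the high respiratory-rate limit, so for any baseline up to 25 the low row counts every fall of 5 or more

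*SAP*

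**What the plan says.** SAP 15.4 (Vital Signs) gives a list of paired criteria, introduced by "The following potentially clinically significant abnormalities will be summarized". Each blood-pressure, pulse and respiratory-rate criterion has two parts: an absolute limit and a minimum change from baseline.

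For respiratory rate the two entries are:

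- low: "≤ 20 breaths/min and decrease from baseline ≥ 5 breaths/min in respiratory rate"
- high: "≥ 20 breaths/min and increase from baseline ≥ 5 breaths/min in respiratory rate"

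The low entry thus rests on "20 breaths/min and decrease from baseline" and the high entry on the same figure.

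The systolic pair shows the pattern used elsewhere in the list: "≤ 95 mmHg and decrease from baseline ≥ 20 mmHg in systolic blood pressure" for low and "≥ 140 mmHg and increase from baseline ≥ 20 mmHg in systolic blood pressure" for high. Diastolic pressure (45 and 90 mmHg) and pulse (50 and 100 beats/min) are built the same way, with a required change of 20. Weight has only a 10% change in each direction and no absolute limit.

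Neither document gives another low respiratory-rate limit, a normal range, or a reason for sharing one limit. Protocol 8.2.2 has respiratory rate recorded, and the Schedule of Activities (Protocol 1.3) has vital signs taken at each two-weekly treatment visit. SAP 6.1 keeps vital signs among the safety analyses for the abbreviated report.

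**The concern.** A criterion that joins a level to a change is meant to pick out values that are both extreme and shifted. If the low level coincides with the point where the high range starts, the level part has little left to do. The row then behaves as a change-only rule while still being labelled a low abnormality.

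What is at stake is the reading of one row in a descriptive safety table. A reader would take its count as the number of participants with a potentially important low respiratory rate. It would also include participants whose rate came down from a raised baseline, or who simply varied by 5 breaths/min. Because vital signs are measured every two weeks, each participant has repeated chances to meet so loose a rule.

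**Working it through.** The plan states these limits and does not calculate them, so there is no figure to reproduce. The check compares the four pairs and finds when each low limit excludes anything.

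**Inputs** (all from SAP 15.4). L is the low limit, H the high limit, d the required change.

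| Parameter | L | H | d | H − L | L + d |
|---|---|---|---|---|---|
| Systolic pressure (mmHg) | 95 | 140 | 20 | 45 | 115 |
| Diastolic pressure (mmHg) | 45 | 90 | 20 | 45 | 65 |
| Pulse (beats/min) | 50 | 100 | 20 | 50 | 70 |
| Respiratory rate (breaths/min) | 20 | 20 | 5 | 0 | 25 |

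**When the low limit filters.** From baseline b, a fall of at least d ends at b − d or lower. If b − d ≤ L, that is b ≤ L + d, the condition value ≤ L is met automatically. The low limit can exclude a fall only when b > L + d.

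**Comparison with the high limit.** For systolic, diastolic and pulse, L + d lies below H (115 < 140, 65 < 90, 70 < 100). The low limit therefore already filters falls from baselines that the SAP does not treat as high. For respiratory rate, L + d = 25 lies above H = 20. The low limit acts only when the baseline is itself more than 5 above the level at which the SAP's high range begins.

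**Enumeration.** Whole-number baselines from 12 to 30 were run against on-treatment rates from 6 to 40. For every baseline from 12 to 25 the low limit removed none of the falls of at least 5. At 26 it removed one value (21), at 27 two, and at 30 five.

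**Examples under the low rule as written.**

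- 20 to 15: fall 5, 15 ≤ 20, flagged low.
- 22 to 16: fall 6, 16 ≤ 20, flagged low.
- 25 to 20: fall 5, 20 ≤ 20, flagged low, although 20 also meets the absolute part of the high rule.

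**Sensitivity.** The intended limit is not in the documents. For illustration only, with assumed low limits of 8, 10, 12 and 14, the rates flagged today from a baseline of 20 that would stop being flagged are 9–15, 11–15, 13–15 and 15. From a baseline of 22 they are 9–17, 11–17, 13–17 and 15–17. The over-count is present across the whole range, and its extent depends on the limit the sponsor intended.

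**The case against.** Several stronger readings are tempting, and the documents do not support them.

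- **That the plan would miss or hide low respiratory rates.** The limit is too permissive, not too strict. Every low rate with a fall of at least 5 is still flagged. What is lost is specificity. SAP 15.4 also asks for minimum, maximum and quartiles of values and changes at each visit, and for a listing with value and change, so a truly low reading remains visible.
- **That normal rates in general are reported as abnormal.** A rate at or below 20 is flagged only with a fall of at least 5, and the documents give no normal range against which to call a rate normal. The argument above does not need one.
- **That every other vital sign has separate limits.** The contrast holds for systolic, diastolic and pulse. Weight has no absolute limit, and temperature and oxygen saturation have no criterion in the list.
- **That a reading of 20 is counted twice.** One reading cannot be both 5 above and 5 below the same baseline, so the two flags exclude each other.
- **That a rise from 15 to 20 is part of the problem.** It is flagged by the high rule, which changing the low limit would leave as it is.

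Two further points have some weight. SAP 6.1 names vital signs without naming this table, so its production for the abbreviated report is likely but not explicit. And 20 might have been chosen deliberately. But nothing says so, and a limit that has no effect for baselines up to 25 does not fit the form of the three comparable pairs.

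**Conclusion.** The point holds as a specification error in one row. With 20 as the limit in both directions, the low respiratory-rate criterion is a change-only rule for every baseline up to 25. It will over-count low abnormalities and cannot tell them from ordinary falls. This follows from the SAP's own limits without any outside normal range.

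The number of participants affected cannot be stated, because neither document gives a distribution of respiratory rates or the intended low limit. The consequence is confined to a descriptive safety table and any repeat of it for the China sub-population. No efficacy result, decision rule or error rate changes. It is minor, but wrong as written.

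**What to change.** In SAP 15.4, reconcile the two respiratory-rate criteria by replacing the low limit with the one the sponsor intended, distinct from and below the high limit. Make the same change in the table program before the table is produced. The documents do not contain the intended figure, so the sponsor must supply it, and none is proposed here.

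Once the figure is known, the cost is one number in the SAP and one in the program. No new data are needed, since respiratory rate is already recorded.

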15.5 Other Safety or Tolerability Evaluations

ECG

Single 12-lead ECGs will be obtained at screening and repeated during the study if clinically indicated using an ECG machine that automatically calculates the heart rate and measures PR, QRS, QT, and QTc Intervals, and ECG parameters will be derived from the data collected on the “Electrocardiogram” eCRF page.

A listing of ECG values will be provided including participant identifier, age, sex, race, ECG parameter and unit, visit, ECG date, value, change from baseline. Baseline values and post-baseline values collected after the on-treatment period will be flagged. Qualitative ECG results will also be provided in the listing.

ECOG Performance Status (ECOG PS)

The ECOG PS will be derived from the data collected on the “ECOG Performance Status” eCRF page.

The ECOG shift from baseline to the highest score during the on-treatment period will be summarized.

ECOG PS will also be presented in a listing at each timepoint.

Non-protocol Related Hospital Visits

Participant’s non-protocol related hospital visits will be listed from data collected on the “Non Protocol Related Hospital Visit” eCRF page. The listing will include participant identifier, age, sex, race, visit, total number of pre-planned ambulant (outpatient) hospital visits since the last study visit, total number of unplanned ambulant (outpatient) hospital visits since the last study visit, total number of nights spent in the hospital for pre-planned overnight (inpatient) hospital visits since the last study visit and total number of nights spent in the hospital for unplanned overnight (inpatient) hospital visits since the last study visit.

16 Analyses of Other Endpoints

16.1 Pharmacokinetics

The analyses described in this section will be performed by the Clinical PK/PD group (CPK) of Translational Medicine, Merck Healthcare KGaA, Darmstadt, Germany, or by a Contract Research Organization selected by the Sponsor. Pharmacokinetic listings and individual data will be presented based on the SAF. Summaries and statistical analyses will be based on the PKAS. Only subgroup sample size with a minimum of 3 subjects will be displayed.

Pharmacokinetic samples to be collected were specified in Section 1.3 of the protocol. Pharmacokinetic concentrations/parameters refer to bintrafusp alfa concentrations/PK parameters.

16.1.1 Missing/non-quantifiable Pharmacokinetic Data Handling

Concentrations below the lower limit of assay quantification

Pharmacokinetic concentrations below the lower limit of quantification (<LLOQ) will be set to zero for calculating parameters and descriptive statistics.

Deviations, missing concentrations, and anomalous values

There will be no imputation of missing data. Concentrations will be set to missing in summary tables if the value is reported as no result. Pharmacokinetic concentrations which are erroneous due to a protocol violation (as defined in the clinical study protocol), documented handling error, or analytical error (as documented in the bioanalytical report) may be excluded from the PK analysis if agreed upon prior to performing a statistical analysis. In this case the rationale for exclusion must be provided in the CSR and/or relevant listing/table.

Exclusions for concentration data (and C_{EOI}/C_{trough}) descriptive statistics

- Positive pre-dose values on Day 1
- Concentration observed at the end of infusion (C_{EOI}) <LLOQ
- In case of missed dose, exclude all concentrations until intended dosing is resumed
- Concentration observed at the end of the dosing interval (C_{trough}) values in case samples are taken at least 7 days late or early

Any other PK concentrations that appear implausible to the Pharmacokineticist/PK Data Analyst must not be excluded from the analysis. Any implausible data will be documented in the CSR and/or relevant listing/table.

If a PK parameter cannot be derived from a participant's concentration data, the parameter will be coded as "NC" [not calculated (NC)]. Note that NC values will not be generated beyond the day that a participant discontinues the treatment. For statistical analyses, PK parameters coded as NC will be set to missing.

If an individual participant has a known biased estimate of a PK parameter (due for example to a deviation from the assigned dose level), this participant/value will be excluded from the descriptive statistics, and instead the result will be listed only.

Relevant decisions on participant inclusion in the PKAS will be made before database lock in the Database Review Meeting.

16.1.2 Descriptive Pharmacokinetic Analysis

Presentation of PK Concentration Data

A by-participant listing will present PK sample times, time deviations, and concentrations based on the SAF. Concentrations will be reported with the same precision as the source data.

Presentation of PK Parameter Data

The PK parameters listed below will be taken directly from the observed bintrafusp alfa concentration-time data.

C_{EOI}	The concentration observed immediately at the end of infusion.
C_{trough}	The concentration observed immediately before next dosing (corresponding to pre-dose or trough concentration for multiple dosing).

RC_{EOI}	Accumulation ratio for C_{EOI} . Calculated as C_{EOI} Day 29 / C_{EOI} Day 1.
RC_{trough}	Accumulation ratio for C_{trough} . Calculated as C_{trough} Day X / C_{trough} Day 15. All applicable visits.

Individual PK C_{trough} and C_{EOI} will be listed by nominal study day based on the SAF. Individual PK C_{trough} and C_{EOI} will be reported with the same precision as the source data. Accumulation ratios will be reported with 3 significant figures.

Pharmacokinetic parameter data will be presented in tables and descriptively summarized by nominal study day using: n, Mean, StD, coefficient of variation (CV%), Min, Med, Max, geometric n, geometric mean (GeoMean), StD of log-transformed data (logStD), the geometric coefficient of variation (GeoCV%), and the 95% CI for the GeoMean (LCI 95% GM, UCI 95% GM). Summaries will be based on the PKAS. At least 3 values for a summary category will be required for descriptive statistics to be calculated. If $n = 2$, these will be presented as Min and Max. If $n < 2$, only n will be presented. Only subgroup sample size with a minimum of 3 subjects will be displayed.

Additional table(s) will summarize PK concentrations with further stratification by ethnicity (e.g., Japanese, non-Japanese Asian, all Asian, non-Asian, Chinese mainland, non-Chinese mainland Asian), based on the PKAS. Additional table(s) will summarize C_{trough} and C_{EOI} with further stratification by ADA subsets ever positive and never positive, based on the PKADA and . Additional table(s) will summarize C_{trough} and C_{EOI} with further sub-stratification by nAb subsets ever positive and never positive, based on the PKNAB. For nAb subsets, summaries will be done for ever positive in either of 2 nAb assays (PD-L1 and TGF β receptor neutralization; PD-L1+/TGF β +, PD-L1+/TGF β -, PD-L1-/TGF β +) versus never positive (PD-L1-/TGF β -). Additional table(s) will summarize C_{trough} of ADA “Treatment emergent (ALL)” versus “ADA Non-Treatment-emergent”, based on the PKADA. Additional table(s) will summarize C_{trough} of ADA Treatment-emergent (ALL) subjects and nAb Treatment-emergent subjects by PK day relative to seroconversion, based on the PKADA and PKNAB, respectively. Additional table(s) may summarize C_{trough} and C_{EOI} with (further) stratification by race (Asian versus nonAsian) and ethnicity (e.g. Japanese, Chinese, etc.) subgroups or prior Bevacizumab use (Bevacizumab used versus Bevacizumab not used), as appropriate. Only subgroup sample size with a minimum of 3 subjects will be displayed.

In export datasets, as well as in the SDTM PP domain, PK parameters will be provided with full precision (i.e., as much as allowed by software) and will not be rounded. Descriptive statistics of PK parameter data will be calculated using full precision values and rounded for reporting purposes only.

The following conventions will be applied when reporting descriptive statistics of PK parameter data:

- Mean, Min, Med, Max, GeoMean, 95% CI: 3 significant digits
- StD, logStD: 4 significant digits
- CV%, GeoCV%: 1 decimal place

Individual PK C_{trough} and C_{EOI} values will be plotted versus actual study day on a linear scale, for all participants. Individual data will be presented based on the SAF.

Arithmetic mean (\pm StD), GeoMean (\pm logStD), and Med C_{trough} and C_{EOI} will be plotted versus nominal study day on a linear scale. Summaries will be based on the PKAS.

Additional figures will present Mean, GeoMean, and Median PK concentration-time profiles with further stratification by ethnicity (e.g., Japanese, non-Japanese Asian, all Asian, non-Asian, Chinese mainland, non-Chinese mainland Asian), based on the PKAS. Additional figure(s) will present Mean, GeoMean, and Med C_{trough} and C_{EOI} with further stratification by ADA subsets ever positive and never positive, based on the PKADA, as long as both subsets consist of 3 or more participants. Additional figure(s) will present Mean, GeoMean, and Med C_{trough} and C_{EOI} with further sub-stratification by nAb subsets ever positive and never positive, based on the PKNAB, as long as both subsets consist of 3 or more participants. Additional figure(s) may summarize C_{trough} and C_{EOI} with (further) stratification by ethnicity (e.g., Japanese, Chinese, etc.) subgroups, as appropriate. Only subgroup sample size with a minimum of 3 subjects will be displayed.

For ADA treatment-emergent (ALL) subjects with at least one C_{trough} measurement before and on/after ADA seroconversion, individual C_{trough} will be plotted versus PK day relative to seroconversion (for readability, split further into groups of 10 subjects or fewer as needed), based on the SAF. Box plots will be prepared for C_{trough} versus PK day relative to seroconversion, based on the PKADA. Additional figure(s) may summarize C_{trough} with (further) stratification by race (Asian versus non-Asian) and ethnicity (e.g. Japanese, Chinese, etc.) subgroups or prior Bevacizumab use (Bevacizumab used versus Bevacizumab not used), as appropriate. Only subgroup sample size with a minimum of 3 subjects will be displayed.

For nAb treatment-emergent subjects with at least one C_{trough} measurement before and on/after nAb seroconversion (earliest of 2 assays if positive in both), individual C_{trough} will be plotted versus PK day relative to seroconversion (for readability, split further into groups of 10 subjects or fewer as needed), based on the SAF. Box plots will be prepared for C_{trough} versus PK day relative to seroconversion, based on the PKNAB. Additional figure(s) may summarize C_{trough} with (further) stratification by ethnicity (e.g., Japanese, Chinese, etc.) subgroups, as appropriate. Only subgroup sample size with a minimum of 3 subjects will be displayed.

CCI

CCI

CCI

CCI

CCI

CCI

CCI

CCI

16.4 Immunogenicity

16.4.1.1 Antidrug Antibody

Analysis Sets: IMM

The ADA results will be derived for each visit based on the algorithm in [Table 14](#).

Table 14 Algorithm for the Derivation of ADA Results

Sample Screen Result	Confirmatory	Titer	ADA Result
Negative	NA	NA	Negative
NR	NA	NA	NR
Positive	Negative	NA	Negative
Positive	NR	NA	NR
Positive	Positive	Number	Number
Positive	Positive	NR	Positive-TNR

NR = no result, NA = not applicable, TNR = titer no result.

Note that samples collected during and after the on-treatment period (e.g. safety follow-up) including the ones collected during the reinitiation period will be included in the analysis. Negative, number, or positive-TNR are valid results while number and positive-TNR are considered as positive. Participants will be characterized into different categories based on the criteria in [Table 15](#).

Table 15 **Participants Characterized based on ADA Results**

Category	Definition	Participant at Risk (Denominator for Incidence)
Never positive	No positive results at any time point	Number of participants with at least one valid result at any time point
Ever positive	At least one positive result at any time point, including baseline	Number of participants with at least one valid result at any time point
Pre-existing	A positive ADA result prior to treatment with bintrafusp alfa	Number of participants with valid baseline result
Treatment boosted	A positive ADA result prior to treatment with bintrafusp alfa and at least one post-baseline value with ADA titer result $\geq 8 \times$ baseline ADA titer result	Number of participants with valid baseline result and at least one valid post-baseline result
Treatment emergent (induced)	Not positive prior to treatment with bintrafusp alfa and with at least one positive post-baseline result	Number of participants with at least one valid post-baseline result and without positive baseline result (including missing, NR)
Treatment emergent (ALL)	Treatment-emergent plus treatment-boosted	Number of participants with at least one valid post-baseline result at any timepoint
ADA Non-Treatment-emergent	All subjects minus treatment-emergent All	Number of participants with at least one valid post-baseline result at any time point
Transient positive	If treatment emergent participants have - a single positive evaluation and last assessment not positive or - duration between first and last positive result < 16 weeks and last assessment not positive	Number of participants with at least one valid post-baseline result and without positive baseline result (including missing, NR)
Persistent positive	If treatment emergent participants have duration between first and last positive result ≥ 16 weeks or a positive evaluation at the last assessment	Number of participants with at least one valid post-baseline result and without positive baseline result (including missing, NR)

Start of Immunogenicity Response

For participants with any positive ADA response, the date of the first assessment with positive ADA result will be considered as start date of ADA response.

Time to onset (weeks) of ADA response will be calculated as:

$$(\text{Date of first positive ADA assessment} - \text{start date of bintrafusp alfa treatment} + 1) / 7$$

Note: If the first positive is prior to the start of treatment, the formula is revised to:

(Date of first positive ADA assessment – start date of bintrafusp alfa treatment) / 7

Duration of Immunogenicity Response for treatment-emergent ALL

Duration of ADA immunogenicity response (weeks) is defined as:

- (Date of last positive ADA assessment – date of first positive ADA assessment + 1) / 7 for treatment-emergent participants

(Date of last positive ADA assessment - date of first boosted (titer $\geq 8 \times$ baseline titer) ADA assessment + 1) / 7 for treatment boosted participants

The following analysis will be described:

- The frequency and percentage of each ADA category, as defined in [Table 15](#), will be tabulated
- The ADA titer value by timepoint will be summarized
- The maximum observed ADA titer per participant will be tabulated. For each discrete titer value, percentages will be calculated using the total number of participants in each ADA status group as the denominator
- The time to onset of response for treatment-emergent ALL participants will be summarized
- The duration of ADA immunogenicity response for treatment-emergent ALL participants will be summarized

The following further analyses will also be described:

- Evaluation of potential effect of ADA on bintrafusp alfa safety (see [Section 15.1.1](#))
- Evaluation of potential effect of ADA on bintrafusp alfa efficacy
 - for best overall response according to RECIST 1.1 as adjudicated by IRC (see [Section 14.1.1](#))
 - for progression-free survival according to RECIST 1.1 as adjudicated by IRC (see [Section 14.2.1](#))
 - for duration of confirmed response according to RECIST 1.1 as adjudicated by IRC (see [Section 14.2.8](#))
 - for durable confirmed response according to RECIST 1.1 as adjudicated by IRC (see [Section 14.2.10](#))
 - for overall survival (see [Section 14.2.13](#))
- Evaluation of potential effect of ADA on bintrafusp alfa Pharmacokinetics (see [Section 16.1](#))

Potential effect of ADA on safety, efficacy and PK will be evaluated on ADA positive status (ever positive, never positive).

Listings of ADA results from ever positive participants will be provided with the following: participant ID, age, sex, race, ADA categories status, visit, date of assessment and results of screening, confirmatory and titer values. A further listing will contain: participant ID, age, sex, race, date of first ADA positive result, responder per IRC/investigator, date of response and timing

of response related to the date of first ADA positive result. Responders will be defined as participants meeting confirmed CR or PR and non-responders as all other participants.

